## Blood Samples

Blood samples will be drawn by qualified and trained site personnel and according to the standard operating procedures (SOPs) at the investigational site.

Since the test for nicotine concentration is highly sensitive, precautions should be taken during blood sampling and processing to prevent the contamination of samples with environmental nicotine.

In total, approximately 95 mL of blood will be collected for this study including samples for determination of serology (5 mL), COHb (30 mL) and safety laboratory (approximately 60 mL). This calculation is based on an individual volume of each sample of 20 mL per safety laboratory assessments, 5 mL for serology, and 5 mL for COHb assessment. The total volume of blood drawn (approximately 95 mL) will not exceed the levels for a standard blood donation.

Details on the procedures for collection, labelling, processing, and shipment of samples will be described in the LM/SHM.

## Urine Samples

**Spot urine samples** will be used for the urine drug screen, urine cotinine screen, urine pregnancy test, and safety urine analysis at Screening visit, Admission visit on Day -2, and after completion of 24-hour urine sample collection on Day 6.

**24-hour urine collection** Subjects will discard their first void in the morning of Day -1. The collection period will start immediately after. After 24-hours  $\pm 1$ h of urine collection, subjects will empty their bladder again in the morning of the visit and this urine will be used as the final portion of the 24-hour urine sample.

During the collection period, all urine passed must be collected in the sampling container. No urine should be passed into the toilet. The start and the end time of urine collection will be recorded by the subject and checked by the site staff. The volume of 24-hour urine will be measured by the site staff upon collection of urine containers from the subjects. For assessment of urine BoExp, creatinine aliquots from the 24-hour urine collection will be taken. In the schedule of events for the 24-hour urine collection, the dot corresponds to the day on which the 24-hour urine collection period starts.

## Confidentiality Statement

Data and information contained in this document are considered to constitute trade secrets and confidential commercial information, and the legal protections provided to such trade secrets and confidential information are hereby claimed under the provisions of applicable law. No part of this document may be publicly disclosed without the written consent of Philip Morris Products S.A.

***Biobanking of urine*** If a subject gives optional consent for biobanking, additional samples of urine from the 24-hour collection will be aliquoted. The samples intended for biobanking will be kept frozen and will be shipped to a central storage facility according to the LM/SHM. After the final CSR is signed, samples of urine will be stored for a maximum duration of 2 years.

## 7.4 Other Study Procedures

### 7.4.1 Demonstration of THS and Product Test

All subjects will have a demonstration of THS by the investigational site staff at the Screening visit without product use.

At Admission (Day -2), after enrollment, investigational site staff will inform subjects on product use and subjects will have a product test with THS Blade device and Induction Mono device with up to three sticks per THS for a duration of approximately one hour.

## 7.5 Questionnaires

The study questionnaires will be completed by the subjects in a paper format. All subject-reported measures as well as instructions will be provided in the subject's local language.

### 7.5.1 Tobacco/Nicotine Product Use History

Subjects will be asked questions about their TNP use history. The questions will capture frequency and quantity of TNP use over the past four weeks, the flavor of cigarettes the subjects do smoke, the number of continuous years of CIG smoking, the duration of cessation attempts over the past three years, and the intention to quit smoking within the next 3 months. This information will be used as characteristics of the study subjects, to assess their eligibility to participate in the study, and to serve as baseline values.

### 7.5.2 Fagerström Test for Nicotine Dependence (Revised Version)

Self-reported level of nicotine dependence will be assessed via a questionnaire on Baseline Day -1 using the Fagerström Test for Nicotine Dependence (FTND) in its revised version [23], as updated in 2012 [14]. The questionnaire consists of six questions which will be answered by the subjects. The scores obtained on the test permit the classification of nicotine dependence into three levels: Mild (0-3 points), moderate (4-6 points), and severe (7-10 points) [23]. This information will be used as characteristics of the study subjects.

### 7.5.3 ABOUT–Product Experience Questionnaire

Product experience will be assessed via the ABOUT–Product Experience, a subject self-reported outcome measure part of the ABOUT toolbox [24].

The questionnaire consists of 3 multi-item scales and 2 single-item scales, arising from an adaptation and rewording of the modified cigarette evaluation questionnaire (mCEQ) [15] to RRP and the Product Evaluation Scale [25].

The questionnaire assesses the perceived effects experienced by CIG smokers switching to THS Blade device, Induction Mono device, or Induction Mid device compared to the experience of subjects continuing CIG smoking by measuring:

- Product satisfaction (satisfying, tastes good, enjoy the product).
- Psychological rewards (calms down, more awake, less irritable, helps concentrate, reduces hunger).
- Aversion (dizziness, nausea).
- Enjoyment of respiratory tract sensations (single-item assessment).
- Craving reduction (single-item assessment).

Subjects will be asked to assess the items of the questionnaire on a 7-point scale, ranging from “not at all” to “extremely”. A score for each subscale will be computed based on the scoring rule established by the questionnaire developer [15].

Symptoms or worsening of symptoms documented in the questionnaire do not need to be documented as additional AEs as the main source for AE collection is the face-to-face interview between the subject and study site staff, using open, non-directive questions, as described in section 8.2.1.

## 8 Adverse Events

### 8.1 Definitions

#### 8.1.1 Adverse Events

An adverse event (AE) is defined as any health-related event which is adverse or unfavorable and which either starts after ICF signature or represents a worsening of a health-related condition that existed at the time of that signature. Careful medical judgment is required to establish whether a clinical finding (including an abnormal laboratory result) is a true AE or just a manifestation of a preexisting health-related condition. An AE may or may not have a causal relationship with the study procedures or with the use of investigational product.

#### 8.1.2 Serious Adverse Events

A serious adverse event (SAE) is defined as an AE that:

- Results in death,
- Is life-threatening,
- Requires inpatient hospitalization or prolongation of existing hospitalization,
- Results in persistent or significant disability/incapacity,
- Is a congenital anomaly/birth defect, or
- Is an important medical event.

Important medical events that may not result in death, be life-threatening, or require hospitalization may be considered an SAE when, based on appropriate Investigator's medical judgment, they may jeopardize the subject, or the subject may require medical or surgical intervention to prevent one of the outcomes listed in the above definitions.

"Life-threatening" means that the subject was at immediate risk of death from the event. It might have caused death if it had occurred in a more serious form.

#### 8.1.3 Conditions Existent Before the Start of the Period of Collection (ICF signature)

Concomitant diseases whose severity is increasing after the Screening visit are to be captured as AE or SAE, depending on if any seriousness criterion is met.

Therapies or surgical interventions including admissions to hospital that had been planned before the ICF signature should not be considered AEs/SAEs.

## 8.2 Collection and Reporting of Adverse Events

### 8.2.1 Collection of Information

AEs should be collected mainly via face-to-face interview with the subject by the use of consistent, open, non-directive questions from the investigator(s) or designee(s) (e.g., "How have you been feeling since you were last asked?").

Any non-serious AE occurrence during the study must be documented in the subject's medical records in accordance with the Investigator's normal clinical practice and on the AE page of the CRF. SAEs that occur during the study must be documented in the subject's medical record, on the AE CRF, and on the SAE form for recording into safety database.

Information recorded for AEs/SAEs will include verbatim description, start and stop dates, seriousness, severity (intensity), causal relationship with IP and study procedures, action taken with IP (e.g., reduced, not changed), other action taken (e.g., treatment administered, if led to the subject's discontinuation from the study), and outcome (e.g., resolved, stabilized).

Whenever a medically meaningful diagnosis is available to comprise a set of reported signs and/or symptoms, it should be preferentially provided as the AE or SAE term, rather than the individual signs and/or symptoms.

### 8.2.2 Period of Collection

AEs (including SAEs) will be collected from the time of ICF signature until the individual EOS for each participant.

Any AEs which occur during the Screening period will be captured by the investigational site staff and assessed by the Investigator or designee(s) to establish relationship to study procedures.

During a 3-day Safety follow-up period new AEs/SAEs will be recorded and ongoing AEs/SAEs will be followed-up by the study site, as described in section [8.2.6](#).

### 8.2.3 Intensity of Adverse Event

The Investigator must assess the intensity of each reported AE according to the following grading scale:

#### Table 5 Intensity of Adverse Events

|              |   |
|--------------|---|
| Mild: | Easily tolerated, not interfering with normal everyday activities |
|--------------|---|

#### Confidentiality Statement

Data and information contained in this document are considered to constitute trade secrets and confidential commercial information, and the legal protections provided to such trade secrets and confidential information are hereby claimed under the provisions of applicable law. No part of this document may be publicly disclosed without the written consent of Philip Morris Products S.A.

**Moderate:** Interferes with normal everyday activities, but the subject is still able to function

**Severe:** Incapacitating and requiring medical intervention

#### 8.2.4 Relationship to Investigational Product and Relationship to Study Procedures

The Investigator must assess the causal relationship between the exposure to the IP (THS or CIG) and each of the reported AEs, using the classification system and the criteria described below. The same assessment must be made separately to assess the causal relationship between the study procedures and each of the reported AEs:

**Not related:** The temporal relationship of the adverse event to IP administration or study procedure(s) makes a causal relationship unlikely, or concomitant medication, therapeutic interventions, or underlying conditions provide a sufficient explanation for the observed event.

**Related:** The temporal relationship of the adverse event to IP or study procedure(s) makes a causal relationship possible, and concomitant medication, therapeutic interventions, or underlying conditions do not provide a sufficient explanation for the observed event.

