### Name of Investigational Products:

THS Blade device  
THS Induction Mono device  
THS Induction Mid device  
Subjects' own cigarette brands

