### 6.2.5 Safety Follow-up Period

Following the discharge on Day 6 (or Early termination or discontinuation) and during the subsequent 3-day Safety follow-up period, subjects will be free to use any TNP according to their usual habits.

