9.6.4.4 Adverse Events

AEs (including SAEs) will be collected from the time of ICF signature until the EOS for each participant (AEs occurring on subjects who are not part of the SAF will only be listed and are not part of the summaries related to SAF).

Any AEs which may occur during the screening period will be captured by the investigational site staff and assessed by the Investigator or designee(s) to establish relationship to study procedures.

During a 3-day Safety follow-up period new AEs/SAEs will be recorded and ongoing AEs/SAEs will be followed-up by the study site.

Information recorded for AEs/SAEs will include verbatim description, start and stop dates and times, seriousness, severity (intensity), causal relationship with IP and study procedures, action taken with IP (e.g., reduced, not changed), other action taken (e.g., treatment administered, if led to the subject's discontinuation from the study), and outcome (e.g., resolved, stabilized).

All safety data will be provided in listings by randomized study arm or a group of enrolled but not randomized subjects, subject, and safety period. The safety periods are defined as:

1. Screening: from Screening visit to baseline
2. Exposure: from Day 1 to Day 5 11:00 PM or early discontinuation date and time
3. Follow-up: from end of exposure to end of Safety follow-up

Unless otherwise specified, summaries will be produced by randomized study arm or a group of enrolled but not randomized subjects and safety periods.

Adverse event data will be used for the primary assessment of safety. Other safety variables monitored in this study will include vital signs (systolic and diastolic blood pressure, pulse rate, respiratory rate), ECG data, spirometry data, clinical chemistry, hematology, urine analysis safety panel, concomitant medications.

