The number and percentage of subjects with AEs and SAEs will be tabulated by the Medical Dictionary for Regulatory Activities (MedDRA) system organ class (SOC) and preferred term (PT) for the SAF, overall and by safety period. The number of AEs and SAEs by relatedness to product exposure (including expectedness) and relatedness to study procedures, AEs by severity, and AE by action taken related to the product will be summarized. The number of subjects experiencing an event and the number of events for the SAF will be tabulated. Common adverse events will also be tabulated. Common AEs would be those AEs that have PTs with incidence $\geq 5\%$ in any of the randomized study arms or group of enrolled but not randomized subjects.

Confidentiality Statement

Data and information contained in this document are considered to constitute trade secrets and confidential commercial information, and the legal protections provided to such trade secrets and confidential information are hereby claimed under the provisions of applicable law. No part of this document may be publicly disclosed without the written consent of Philip Morris Products S.A.

Unless specified otherwise, results will be sorted alphabetically by SOC, and by decreasing frequency of the PTs within a SOC. In the event of PTs having equal frequencies, the PTs will be sorted alphabetically within the SOC.

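### An AE judged product-related is not tied to a named product, so outside the Exposure-period tables it may not refer to the product of the arm it is listed under

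*Protocol*

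**What the plan says.** The protocol synopsis lists "Subjects' own cigarette brands" among the investigational products and does not limit this to the CIG arm. On causality, protocol 8.2.4 says "The Investigator must assess the causal relationship between the exposure to the IP (THS or CIG) and each of the reported AEs", with two possible answers, related and not related. A separate judgement covers study procedures. The items to be recorded for each AE (protocol 8.2.1) include "causal relationship with IP and study procedures, action taken with IP (e.g., reduced, not changed"). Neither that list nor its counterpart in SAP 9.6.4.4 has an item for the suspected product.

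On the window, protocol 8.2.2 says "AEs (including SAEs) will be collected from the time of ICF signature until the individual EOS for each participant". For the Screening period it adds that AEs are "assessed by the Investigator or designee(s) to establish relationship to study procedures". After Discharge, "subjects will be free to use any TNP according to their usual habits" (protocol 6.2.5).

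On reporting, SAP 9.6.4.4 plans to summarize "The number of AEs and SAEs by relatedness to product exposure (including expectedness) and relatedness to study procedures". Its default layout is that "summaries will be produced by randomized study arm or a group of enrolled but not randomized subjects and safety periods". The periods are Screening (Screening visit to baseline), Exposure (Day 1 to Day 5 11:00 PM, or early discontinuation) and Follow-up (the remainder).

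Protocol 8.2.5 judges the expectedness of any AE related to THS or CIG against one Investigator's Brochure, which the reference list titles as that for the Tobacco Heating Systems.

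**The concern.** AEs are the main assessment of safety in both documents. A reader who wants to know what harm goes with Blade, Mono or Mid will look at the related AEs under each arm. That reading needs the flag to refer to the arm's own product. As written, the flag means related to at least one investigational product, and each subject has used several of them within the AE window. If the suspected product is not recorded at the time, it can be recovered later only by querying the investigator. Expectedness has the same weakness: for an AE thought to be due to cigarettes, the reader cannot tell that a THS document was the yardstick.

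**Working it through.** No power or error-rate calculation applies, so the check sets product use, safety period and table column side by side. The inputs are protocol 4.1, 6.2, 6.5.1, 7.4.1 and 12.7, and SAP 9.6.4.4.

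| AE onset | Products used | Safety period | What a related flag can mean |
|---|---|---|---|
| Day -2 | Own CIG; Blade and Mono test | Screening | CIG, Blade or Mono, whatever the later arm |
| Day -1 | Own CIG | Not clearly stated | CIG, or a late effect of the test |
| Day 1 to Day 5 11:00 PM | Assigned product only | Exposure | Assigned product, apart from carry-over from Day -1 |
| Day 5 11:01 PM to end of Day 6 procedures | None (abstinence) | Follow-up | Late effect of the assigned product |
| After Discharge to Day 9 | Any product | Follow-up | Late effect of the assigned product, or resumed CIG if that still counts as investigational product |

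**Exposure period.** The column and the flag agree, apart from carry-over early on Day 1.

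**Screening period.** They need not agree. Under Mid, a related AE from Day -2 cannot be due to Mid at all, because Mid is not in the product test. Under CIG, it may be due to a Blade or Mono test stick. Three products are used on the same day, so the onset date alone does not separate them.

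**Day -1.** Screening runs to baseline and Exposure starts on Day 1, while protocol 4.1 defines Baseline as Day -1 06:30 AM to Day 1 06:29 AM. The safety period for this full cigarette day therefore has to be inferred.

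**End of Exposure.** The boundary is a clock time. Protocol 8.2.1 lists start and stop dates only; SAP 9.6.4.4 lists dates and times.

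**Pooled displays.** Protocol 12.7 and SAP 9.6.4.4 plan the tables by system organ class and preferred term overall as well as by period. For the relatedness summary, pooling is neither stated nor excluded.

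**Scale.** Day -2 to Day 9 is 2 + 9 = 11 study days, as there is no Day 0. A THS subject is on the assigned product for 5 of them, so 11 - 5 = 6 lie outside it. This counts days, not AEs. Each arm has 80/4 = 20 subjects, so if all are in the Safety Set, one subject is 1/20 = 5% of a column.

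**The case against.** The strongest reply is the default layout. Summaries are by arm and by safety period, so AEs starting on Day -2, Day -1 or Day 7 stay out of the Exposure-period columns, which are the natural place to read harm from each device. This stands. A reader might infer that AEs caused by own cigarettes before Day 1 or after Day 6 are counted as THS-related. The documents do not prescribe that for the Exposure tables, and they do not explicitly plan a pooled relatedness table. The table shells are a separate document that is not available here.

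A reader might also turn the day count into a share of misattributed AEs. That needs AE rates on each product, and the documents give none. Nor do they support the idea that the THS and CIG columns are made to look alike. Events before Day 1 precede knowledge of the allocation and, by randomization, are expected equally in all arms. In a pooled table they can dilute a ratio, but they do not bias the difference between arms.

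Other replies stand in part:

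- THS or CIG can be read arm by arm as the assigned product. Section 8.2.4 does not say so, and it applies to each reported AE.
- Section 8.2.2 mentions only study procedures for Screening-period AEs. But protocol 4.1 ends the Screening period on Day -3, so Day -2 is not clearly covered.
- It is unsettled whether a cigarette smoked after Discharge, not dispensed by the site, is still investigational product.
- Product logs help to place an onset against use. They do not extend past Discharge, and they cannot resolve Day -2 overlap or carry-over.
- The AE items are a list of what is included, and the case report form is not available. It may already hold a product field. For device events, SAP 9.6.4.5 does list the device type.

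**Conclusion.** The point holds as a gap in data collection and reporting. The related flag names no product. In the Screening and Follow-up displays, and in any display pooled over periods, it can refer to a product other than the arm's own: CIG or a test device under a THS arm, or a THS test device under CIG. The Exposure-period columns are sound apart from carry-over.

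The number of AEs affected is unknown. Safety is descriptive, with no inferential tests, and the primary and key secondary biomarker analyses are untouched. This is a cheap improvement and does not threaten the trial's conclusions. It rests on two assumptions: that the case report form follows the listed AE items, and that section 8.2.4 is applied as worded.

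**What to change.** In protocol 8.2.4 and on the AE page, record the suspected product or products for each AE judged related: own CIG, Blade, Mono, Mid, with more than one allowed. State whether cigarettes smoked after Discharge count as investigational product. State which product's reference information applies when expectedness is judged under 8.2.5.

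In SAP 9.6.4.4, summarize AEs related to the assigned product with onset after first use on Day 1 separately from AEs related to another study product. Say which safety period Day -1 belongs to.

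The cost is one extra field, one extra table row and a judgement call by the investigator for Day -2 events. If the case report form is already closed, a row based on onset still helps, but product attribution would then need queries to the investigator.

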#### 8.2.5 Expectedness

Any AE assessed as related to the IP (THS or CIG) will be assessed for its expectedness. An AE will be regarded as “unexpected” if its nature or severity is not consistent with information already recorded in section 6.7 of the current Investigator’s Brochure [6].

